### **Subject-Rated Behavioral Measures (or Parent/Guardian rated if the subject is <18 years of age)**

*(Administered at screening evaluation)*

- Demographic Interview: This brief interview will collect information regarding socioeconomic status and history of head injury or trauma [27].

*(Administered at baseline, midpoint, and final study visits)*

## Photobiomodulation in ASD

- Social Responsiveness Scale-Second Edition Self-Report (SRS-2; [28]): a 65-item rating scale completed by subjects that is used to measure the severity of autism spectrum symptoms as they occur in natural settings.
- Adult ADHD Self-Report Scale (ASRS; [29]): The 18-item ADHD Rating Scale will be completed to evaluate frequency of ADHD symptoms on a scale of 0 to 4.
- Behavior Rating Inventory of Executive Function-Adult Self-Report Version (BRIEF-A; [30]): a 78-item rating scale to assess level of executive function deficits.
- Behavior Rating Inventory of Executive Function-Parent Report Version (BRIEF-P): a 78-item rating scale to assess level of executive function deficits.
- Quality of Life Enjoyment and Satisfaction Questionnaire (Q-LES-Q; [31]): a 16-item questionnaire to evaluate the degree of enjoyment and satisfaction experienced in eight areas of daily functioning.

### **Observer-Rated Behavioral Measures (or Parent/Guardian rated if the subject is <18 years of age)**

*(Administered at baseline and endpoint)*

- Social Responsiveness Scale-Second Edition Informant-Report (SRS-2; [28]): a 65-item rating scale completed by parents/caregivers that is used to measure the severity of autism spectrum symptoms of the subjects as they occur in natural settings.
- Adult Behavior Checklist (ABCL; [32]): An observer-rated assessment of maladaptive behavioral and emotional problems, social competence and substance use in adults ages 18-59.
- Child Behavior Checklist (CBCL): A parent-rated assessment of maladaptive behavioral and emotional problems, social competence, and substance use in children.

*(Administered at baseline, midpoint, and endpoint)*

- MGH Social-Emotional Competence Scale [Informant-Rated Measure] (MGH-SECS-I): This is a 37-item scale that assesses change in the frequency and severity of core and associated symptoms of ASD.

### **Clinician-Rated Safety Measures**

*(Administered at baseline, all treatment visits and at final visit)*

- Clinician-Rated Treatment Emergent Adverse Events Log (CTAE): to record any spontaneous adverse health events experienced during the study, along with duration, severity, cause, treatment, and outcome.
- Concomitant Medications: to record additional medications taken during the study.

### **Subject-Rated Safety Measures**

*(Administered at weeks 3 and 6)*

- The tPBM Self-Report Questionnaire (TSRQ) – An open-ended questionnaire focusing on potential inconveniences and discomforts related to the tPBM. It will be offered at week 3 and week 6 of the study (after at least two tPBM sessions have been delivered).

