## 7. DESIGN

**Primary outcome measure** will be reduction in ASD symptoms as measured by change from baseline on the self- and/or observer-rated Social Responsiveness Scale-Second Edition (SRS-2) and by the clinician-rated CGI-ASD-Improvement score at endpoint. Responders will be defined as those who demonstrate a  $\geq 30\%$  reduction in SRS-2 total score and/or CGI-ASD-Improvement score  $\leq 2$ .

**Secondary outcome measures** will assess for:

1. Treatment-related changes in associated psychopathology, social cognition, executive functions will be assessed by:
  - MGH Social-Emotional Competence Scale (MGH-SEC Scale; clinician- & observer-rated)
  - Social Responsiveness Scale-Second Edition (SRS-2; self- & observer-rated)
  - Adult Behavior Checklist (ABCL; self- & observer-rated) or CBCL where applicable
  - Behavior Rating Inventory of Executive Function-Adult Self Report Version (BRIEF-A) or parent version (BRIEF-P) for youth
  - Adult ADHD Self-Report Scale (ASRS) & clinician-rated Adult ADHD Investigator Symptom Report Scale (AISRS) and CGI-ADHD scale
  - Quality of Life Enjoyment and Satisfaction Questionnaire (Q-LES-Q)
  - Hamilton Anxiety scale (HAM-A) & clinician-rated CGI-Anxiety scale
  - Hamilton Depression scale (HAM-D) & clinician-rated CGI-Depression scale
2. Safety and tolerability will be assessed by:
  - The monitoring of spontaneous treatment-emergent adverse events with the Clinician-rated Treatment-emergent Adverse Events Log (CTAE)
  - tPBM Self-Report Questionnaire (TSRQ)

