### **Study baseline to Endpoint (week 8)**

Participants will be prescribed to administer 2 treatments per week for 8 weeks. Virtual study visits will have a visit window of +/-3 days to facilitate scheduling. All visits will be conducted virtually via the MGH Telemedicine platform, TeleHealth, which is maintained by Partners HealthCare. In the event that TeleHealth malfunctions or a subject loses access to a device compatible with TeleHealth at scheduled time, the study visit will be completed via telephone call instead.

During the visits, the participants will be asked questions about the symptoms of ASD and general health in addition to any present side effects or changes in their medications. At weeks 2, 4 (Midpoint), and 6 the participant will be asked to fill out questionnaires.

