### During study visits:

- A study doctor will ask the participant questions about the participant's ASD symptoms and general health. The study doctor will also ask if the participant is having any side effects, and if they have taken any other medications during the previous week (see Table I for details).
- We will ask the participant to fill out five questionnaires at baseline (beginning of Week 1) and midpoint (end of Week 4) and this will take approximately 30 minutes. We will ask participant to fill out one questionnaire on beginning of weeks 3, and 6 (approximately 5-10 minutes). We will ask participant to fill out six questionnaires at endpoint (approximately 40 minutes). For children under the age of 18, we will ask their parent/guardian to complete these forms.
- Optional: If a parent/caregiver is available, we will ask them to complete three observer- & self-rated measures on the REDCAP at baseline and endpoint. The observer-rated MGH Social Emotional Competence Scale (MGH-SECS-I) will also be administered at midpoint. Aside from the observer-rated MGH-SECS-I, any measures that were completed during the screening visit (week 99) will only be completed again at endpoint.

For quality control purposes, assessments completed during these visits may be recorded. These recordings will be used to monitor quality control and inter-rater reliability in this study. Each recording will be coded with subject initials and an identification number to maintain confidentiality. These recordings will be stored in a password-protected database or on an encrypted external hard drive stored in a locked filing cabinet in a secure office.

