## Photobiomodulation in ASD

A participant may withdraw consent at any time for any reason (e.g., lack of efficacy, adverse events, etc.). A subject may be withdrawn from the study at any time if any of the following conditions are met:

- Worsening of ASD or current/emergent major psychiatric disorder.
- Subjects who experience intolerable adverse effects as determined by the PI.
- Emergent suicidality
- Pregnancy
- Failure to keep study appointments for more than 2 consecutive visits
- Clinical judgment of the investigator

Those subjects who terminate study participation before the completion of the study will be asked to complete all tasks scheduled to take place on the final study visit at the time of study discontinuation.

Subjects may receive three clinical follow-up visits at the completion of the study (or if they are required to discontinue for safety reasons), allowing adequate time for appropriate psychiatric referrals to treaters in their communities. Follow-up visits are optional and are at no cost to participants. These visits are not part of the clinical trial and no research data will be collected during follow-up. Subjects who fail to keep study appointments, or are non-compliant may be dropped from the study. These study subjects will be given a referral to treaters in their area but will not be offered three follow-up visits.

If a subject would like us to forward their clinical history to his/her primary care physician, or a new clinician, we will forward any pertinent information with the proper completed release of information authorization form. If a subject who has come from the clinic of the investigator happens to drop out of the study, he or she will return to his or her treating physician.

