**Table I. Study Schema**

Weeks	99	0	1	2	3	4	6	8
tPBM Device Subject Training	X	X						
tPBM Treatment (9-17)- 10 min/day		X						
tPBM Treatment (9-17)- 20 min/day			X					
tPBM Treatment (9-17)- 30 min/day				X				
tPBM Treatment (9-17)- 40 min/day					X	X	X	X
tPBM Treatment (18-59)- 20 min/day		X						
tPBM Treatment (18-59)- 30 min/day			X					
tPBM Treatment (18-59)- 40 min/day				X				
tPBM Treatment (18-59)- 50 min/day					X	X	X	X
Diagnostic Assessments								
MGH-ASD-SCL	X							
Psychiatric Evaluation & Medical History	X							
Physiological Procedures								
Physical Examination	X							X
Urine pregnancy test (females only)	X							X
Vital Signs (Height & weight)	X							X
Clinician-Rated Assessments								
MGH-SECS-C		X				X		X
CGIs	X	X		X		X	X	X
GAF	X	X		X		X	X	X
HAM-A	X					X		X
HAM-D	X					X		X
AISRS	X					X		X
CTAE		X		X		X	X	X
Concomitant Medications	X	X		X		X	X	X
Progress Note	X	X		X		X	X	X
Patient-Rated Assessments								
Demographic Interview	X							
ASRS (18+)		X				X		X
SRS-2 (Self/Informant)	X	X				X		X
BRIEF-A/P		X				X		X

Photobiomodulation in ASD

Q-LES-Q		X				X		X
TSRQ				X			X	
MGH-SECS-I (Observer)	X	X				X		X
ABCL/CBCL	X	X						X

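### The self-report tolerability questionnaire (TSRQ) is not given at week 8 or early termination, so early leavers give no self-report of late discomfort or of any, and no one gives one for weeks 6 to 8

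*Combined protocol and SAP*

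**What the plan says.** Section 7 (Design) lists two instruments for safety and tolerability: the clinician's adverse events log (CTAE) and the "tPBM Self-Report Questionnaire (TSRQ"). Section 8, under Subject-Rated Safety Measures, describes the TSRQ as an open-ended form about inconvenience and discomfort from the device, and sets its timing: "It will be offered at week 3 and week 6 of the study (after at least two tPBM sessions have been delivered").

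Table I marks the TSRQ at weeks 2 and 6 and leaves week 8 blank. The text on the treatment period agrees with the table rather than with Section 8: "At weeks 2, 4 (Midpoint), and 6 the participant will be asked to fill out questionnaires".

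On early termination, Section 7 says that subjects who leave before completion "will be asked to complete all tasks scheduled to take place on the final study visit at the time of study discontinuation".

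The CTAE has wider coverage: "Administered at baseline, all treatment visits and at final visit". Its purpose is "to record any spontaneous adverse health events experienced during the study, along with duration, severity, cause, treatment, and outcome". At visits, "The study doctor will also ask if the participant is having any side effects".

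**The concern.** The assessments for early leavers are defined by what the final visit contains. The TSRQ is not in it, so the form is skipped for exactly the group whose view of the device matters most. Section 7 names intolerable adverse effects as a ground for withdrawal, so a missing TSRQ may be related to what it would have said.

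Efficacy is handled differently. Section 9 compares baseline with the last assessment, including a drop-out visit, so a leaver contributes efficacy scores but no self-reported tolerability at that visit.

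At stake is the descriptive account of how participants found the device. Sections 1 and 2 make acceptability and tolerability study questions, and the age range now includes 9 to 17. With up to 20 exposed, a few absent accounts can change that description.

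**Working it through.** The plan states no dropout rate, TSRQ score or TSRQ analysis, so there is no figure of its own to reproduce. The check is a reading of the schedule, followed by a labelled illustration.

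**1. Schedule.** The columns of Table I are weeks 99, 0, 1, 2, 3, 4, 6 and 8. Read by column position:

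| Instrument | Table I | Section 8 |
|---|---|---|
| TSRQ | 2, 6 | 3, 6 |
| CTAE | 0, 2, 4, 6, 8 | baseline, treatment visits, final visit |

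**2. Is the TSRQ hidden in the endpoint count?** The text on study visits announces six questionnaires at endpoint. Table I marks six patient or observer forms at week 8: ASRS, SRS-2, BRIEF-A/P, Q-LES-Q, MGH-SECS-I and ABCL/CBCL. The count is already full without the TSRQ.

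**3. What each kind of participant provides under the plan.**

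| Course | TSRQ forms due | CTAE at last visit |
|---|---|---|
| Leaves the study before the first TSRQ | 0 | yes |
| Leaves between the two TSRQs | 1, silent on anything later | yes |
| Stops the device but stays enrolled | both remain scheduled | yes |
| Completes week 8 | 2, none after week 6 | yes |

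**4. Coverage of the longest sessions.** Tables II and III allow the top duration from day 21. Week 8 ends on day 56, so up to 56 − 21 = 35 days may be spent there. If the first TSRQ is at week 2 or the start of week 3, the week 6 form is the only one that covers this period. The 35 days are a ceiling, because both tables give maxima and the titration is flexible.

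**5. Direction of the effect (illustration; every count except 20 is assumed).** Treat the open-ended form as yes/no for discomfort, which the plan does not define. Let n = 20 be exposed, k = 2 stayers have discomfort, and d participants leave with new discomfort after the first TSRQ and before week 6.

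- Week 6 TSRQ among those remaining: k/(n − d)
- All exposed: (k + d)/n

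| d | Week 6 TSRQ | All exposed |
|---|---|---|
| 0 | 2/20 = 10.0% | 2/20 = 10% |
| 1 | 2/19 = 10.5% | 3/20 = 15% |
| 2 | 2/18 = 11.1% | 4/20 = 20% |
| 4 | 2/16 = 12.5% | 6/20 = 30% |

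With no such leavers there is no distortion, and it grows with each one. A TSRQ at the termination visit recovers the right-hand column if the leavers attend.

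**The case against.** The strongest reply is that little is lost. The CTAE is a final-visit task, so it is completed at termination and records severity and cause. Side effects are asked about, not merely awaited. Section 12 lists discomfort, pain and warmth at the application site among reported adverse events, so the log can capture them. Application sites are inspected at each visit, and subjects are told to contact staff between visits. This stands. A reader might infer that people who leave because of discomfort never report it; the documents do not support that.

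A reader might also infer that anyone who stops using the headband early gives no TSRQ. Section 7 encourages continued enrollment after the device is stopped, so such a participant can still complete the scheduled forms. The gap concerns leaving the study. Those who leave between the two forms have already been offered the first, so only later discomfort is missed.

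Finally, the interim results in Section 1 report 98% adherence and no treatment-limiting side effects, and Section 9 plans no test of the TSRQ. Both points limit the harm. However, the interim results are from adults, adherence is not a dropout rate, and no figure is given for ages 9 to 17.

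The objection does not cover inconvenience that is not an adverse health event, such as the fit of the headband or the burden of daily sessions. Only the TSRQ is designed to collect that.

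**Conclusion.** The schedule gap is certain, on the reading of Table I by column. The only subject-rated tolerability measure is missing at week 8 and therefore at early termination. The loss is the self-reported account, chiefly of inconveniences that would not enter an adverse events log, and the descriptive TSRQ summary can lean toward those who stayed.

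The size cannot be stated. It depends on how many leave the study before week 6 for reasons tied to the device, and the documents give no rate. It would be tempting to assume 3 leavers among 20 and set 3/20 = 15% against 0/17 = 0%. That contrast is not supported: the leavers are assumed, no stayer is allowed any discomfort, and the plan defines no TSRQ rate. Nor do the documents show that five of eight weeks are spent at the longest session.

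This is a modest improvement to a secondary descriptive outcome. It is worth making because it is cheap and reduces missing data that may be informative.

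Separately, Section 8 (week 3) and Table I (week 2) disagree on the first TSRQ. The text on study visits, which places one questionnaire at the beginning of week 3, may explain this, but the places should be reconciled.

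**What to change.** - Add the TSRQ to the week 8 column of Table I, labelled as also applying at early termination, and to the endpoint questionnaires in the text on study visits. Give it to everyone who received at least one session.
- For those who stopped the device earlier but stayed enrolled, word the form to ask about the period on treatment.
- Report TSRQ results with the number exposed and the number missing at each time point.
- State one week for the first TSRQ in Section 8, Table I and the visit text.

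The cost is one more form, 5 to 10 minutes by the protocol's own estimate for the single-questionnaire visits, at a visit that already takes place, plus one REDCap form event. The final visit becomes slightly longer. Leavers who skip the termination visit will still be missing, which is why the missing count should be reported.

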### **10. SAFETY**

Consistent with good clinical practice, safety will be monitored at each study visit by a subject's assigned clinician. This clinician will be available 24 hours a day by page. The principal investigator will supervise all study activities including ratings, reported adverse events, laboratory tests, and vital signs. All procedures have been designed to minimize subject discomfort, and no subject will be asked to engage in research procedures not outlined in the consent form.

If a subject is withdrawn from the study due to adverse events, lack of response, or as a decision by the clinician, they will be offered open treatment for three months, giving adequate time for appropriate psychiatric care to be arranged.

#### **Study Treatment**

Safety will be monitored through treatment-emergent adverse events. Subjects will be monitored for adverse events at each visit. All adverse events will be recorded. A subject may be dropped from the study or dosage may be decreased at any time due to adverse events. All adverse events will be reported to the PHRC according to PHRC guidelines. All concomitant medications will be assessed at every study visit.

### **11. CONFIDENTIALITY**

All research-related records initiated as a result of a subject's participation in this study that reveal the subject's identity will remain confidential except as may be required by law. Subjects will only be contacted regarding future studies if they indicate that they are interested in being contacted by initialing in the specific section of the consent form.

### **12. RISKS AND DISCOMFORTS**

#### **Frequent Adverse Events Related to Study Treatment**

Risks to the subject may include but are not limited to the following:

## Photobiomodulation in ASD

The OLS emits light with a longer wavelength than the human eye can see. Since the OLS is classified as an “Exempt” device in accordance with the requirements of the international standard EN 62471 – Photobiological safety of lamps and lamp systems and, when used correctly, the output is less than the maximum permissible exposure (MPE) no special controls are needed for the environment it is to be used in. The staff will be provided training on basic safety procedures relative to the use of the device.

Failure of the Niraxx Device, resulting in the cessation of investigative therapy can cause:

1. No adverse event to our knowledge
2. Unforeseeable adverse events

Delivery of the infrared LED energy to an inappropriate site, such as directly over the open eye, is not recommended but should pose no risk to the subject:

Based on previous consumer observations, application of the Niraxx may result in mild thermal sensation of warmth during the use. The temperature of the skin is well below the level for thermal damage.

Based on human clinical trial experience to date and sale of the device for its intended use of treating periorbital wrinkles since March 2008, each adverse event listed below has been reported by less than 0.1% of all subjects and users:

1. Application Site Erythema
2. Application Site Pain
3. Application Site Discomfort
4. Application Site Warmth
5. Application Site Reaction
6. Headache

Additional information on adverse events and prior clinical experience can be found in the User Guide. Other potential risks are described below:

Risk of Depression, Suicidality & Manic Switch: Worsening of depression and increased suicidality are possible complications of antidepressant treatments which could be prescribed to subjects with ASD and mood disorders. We will minimize this risk by selecting only subjects who do not present active suicidal ideation at screening. We will also discontinue any subject who develops active suicidal ideation during the course of the study and arrange for appropriate levels of care and standard treatment. Manic switches are possible adverse events and will be closely monitored during treatment as well. Our tight schedule of clinical study visits will allow early recognition of treatment-emergent suicidal ideation or prodromal hypomanic signs. Subjects who develop mania or hypomania will be discontinued and provided appropriate level of care.

Answering detailed questionnaires may create a mild degree of inconvenience for the subjects.

### **Other Adverse Events Related to Study Treatment**

Problems and side effects not listed above and not known at this time could occur. Subjects will be informed of any newly discovered risks as investigators come to learn of such knowledge, if applicable.

### **Risks of Assessments/Questionnaires**

Some questions may make subjects feel uncomfortable because of the nature of the question topics. Some questions ask about possibly sensitive information, including questions pertaining to alcohol and drug abuse. Subjects may refuse to respond to any questions they do not feel comfortable answering.

Adverse events and unanticipated problems will be reported to the PHRC according to current guidelines. We will follow and adhere to all guidelines as defined and outlined on the Partners Human Research Committee web site:

([http://healthcare.partners.org/phsirb/adverse\\_events.htm](http://healthcare.partners.org/phsirb/adverse_events.htm)).

### **13. POTENTIAL BENEFITS**

There may be no direct benefit to subjects participating in this study. Participants may benefit by potentially experiencing improvement in ASD symptoms and by gaining knowledge about ASD.

Study subjects will receive comprehensive clinical assessment of their psychiatric condition. This information will be readily available to their counselors if the subjects agree to disclose. This information might guide counseling in the long term treatment. In the short-term, the subject will receive close and systematic monitoring, beyond current standards of care. Easy access to routine physical exams are also a potential benefit in the community population, which is often underserved. The subjects will have access to a different modality of treatment if counseling was not sufficient and if medications were not acceptable to them. However, there may be no improvement at all, or benefit to participant.

